Primary Effectiveness 1	Communication Success between the S- ICD and EMPOWER PG at 6 Month Visit	95%	88%	One-Sided Lower Pointwise Confidence Limit	2.5%	80%	152 tests/ 38 subjects	30%	220 tests/55 subjects
Primary Effectiveness 2	The percent of subjects with an adequate EMPOWER pacemaker PCT measurement.	95%	80%	One-Sided Lower Confidence Limit	2.5%	90%	57	30%	82

3	Tab	ole of C	Contents						
1.	Тіті	TITLE PAGE1							
2	Pro	ROTOCOL SYNOPSIS6							
3	Тав	LE OF C	ONTENTS						
4	Inte	RODUCTI	ION 21						
•	4.1	Backg	round						
5	Dev	ICE DES	CDIDTION 24						
5	5 1	mCRN	A Coordinated System 24						
	5.1	Imnla	n e oor unateu system						
	53	Non-I	ntable Study Devices 24						
		5.3.1	Non-Implantable Study Devices Associated with the EMPOWER System						
		5.3.2	Model 3870 Programmer Software Application and Associated Firmware25						
		5.3.3	Non-implantable Study Devices Associated with the S-ICD System 26						
	5.4	Access	ories						
	5.5	Additi	onal Equipment27						
6	STU	dy Obje	CCTIVES AND ENDPOINTS27						
	6.1	Study	Objectives						
	6.2	Study	Endpoints						
	6.3	Safety	Endpoints						
	6.4	Effecti	iveness Endpoints						
	6.5	Ancill	ary Objectives						
	6.6	Study	Rationale						
7	STU	DY DESI	GN						
	7.1	Scale a	and Duration						
	7.2	Justifi	cation for the Study Design32						
8	SUB.	JECT SE	LECTION						
	8.1	Study	Population and Eligibility33						
	8.2	Inclus	ion Criteria34						
	8.3	Exclus	sion Criteria35						

9	Subj	ECT AC	COUNTABILITY	36
	9.1	Point o	f Enrollment	36
	9.2	Subjec	t Status and Classification	36
		9.2.1	Intent	36
		9.2.2	Attempt	36
		9.2.3	Partial Implant	36
		9.2.4	Implant	37
	9.3	Access mCRM	to EMPOWER MPS Programmer Software and S-ICD System 1 Programming	ı 37
	9.4	Strateg	gies for Recruitment and Retention	37
	9.5	Withd	rawal	38
	9.6	Lost-to	o-Follow-up	39
	9.7	End-of	-Study Definition	39
	9.8	End of	Study Action Plan	39
10	STUI	ру Метн	HODS	40
	10.1	Data C	Collection	40
	10.2	Enroll	ment Visit	42
		10.2.1	Informed Consent	42
		10.2.2	Enrollment Data	42
		10.2.3	Enrollment Visit Source Documentation Requirements	43
	10.3	Implan	ıt	44
		10.3.1	Implant of the EMPOWER PG	44
		10.3.2	Implant of the S-ICD	48
		10.3.3	S-ICD Firmware Update	50
		10.3.4	mCRM Coordinated System Imaging and Testing	51
		10.3.5	S-ICD Evaluation	56
		10.3.6	S-ICD System Programming Considerations	56
		10.3.7	mCRM Coordinated System Data and Source Documentation Requirements	56
	10.4	Pre-Di	scharge Visit	57
		10.4.1	EMPOWER PG Evaluation	58

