## 9.5 Withdrawal

All subjects enrolled in the clinical study (including those withdrawn) shall be accounted for and documented. If a subject withdraws from the clinical study, the reason(s) shall be

Reasons for withdrawal include, but are not limited to:

- Subject who does not receive either device for the purpose of supporting the study (EMPOWER PG or S-ICD). This includes subjects classified as "Intent", and those classified as "Attempt", according to the definitions in **Section 9.2**.
- Subject found to be ineligible to participate in the study prior to implant of the S-ICD and/ or EMPOWER PG (refer to **Section 9.2** for further information on follow up requirements)
- Physician discretion
- Subject choice to withdraw consent
- Explant of the investigational device(s) (EMPOWER PG and/ or S-ICD converted with clinical firmware) \*; subjects should be followed at least 30 days (either in-clinic or phone contact) post-explant of the mCRM Coordinated System to assure there are no associated adverse events or to assure the resolution of any adverse events associated with the explanted mCRM Coordinated System.
  - **\*Note**: this provision includes explant of the EMPOWER PG in all subjects, and the S-ICD in the case where the device has had clinical firmware uploaded.
- Lost to follow-up
- Death

While study withdrawal is discouraged, subjects may withdraw from the MODULAR ATP Clinical Study at any time, with or without reason, and without prejudice to further treatment. In cases of study withdrawal where the EMPOWER PG remains actively implanted, the subject should be informed that he/she will need to continue to have the EMPOWER PG evaluated per BSC's recommended follow-up (1, 3, 6 months and every 6 months) at a MODULAR ATP Clinical Study site where there is access to the investigational software (Model 3870) to interrogate the EMPOWER PG.

All applicable case report forms up to the point of subject withdrawal and an End of Study Form must be completed in eDC.

Additional study data may no longer be collected after the point at which a subject has been withdrawn from the study or withdraws his/her consent, for whatever reason. All open adverse events should be closed or documented as chronic. Data collected up to the point of subject withdrawal may be used.

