#### 11.1.4 Primary Effectiveness Endpoint 1: Communication Success between the S-ICD and EMPOWER PG at the 6 Month Visit

Primary Effectiveness Endpoint 1 will be assessed at the time of the interim analysis of Safety Endpoint 1 if its null hypothesis is rejected, or at the final analysis if its null hypothesis is not rejected at the interim analysis (refer to **Section 11.3**). The assessment will include subjects who are successfully implanted with both the EMPOWER PG and S-ICD. Effectiveness will be confirmed by evaluating the communication between S-ICD and the EMPOWER PG in four postures: upright, supine, and right and left side. The test unit for this endpoint will be the result from each posture. Communication success will be defined as any evidence of a paced beat during communication testing in a given posture at the initial programmed communication Programmed Telemetry Setting.

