### 11.1.4.2 Sample Size

The sample size estimates were obtained using the normal approximation to the binomial and verified through simulations. The required sample size of 152 tests from a minimum of 38 subjects (220 tests including attrition) was calculated using the following assumptions:

- Performance goal = 88%
- One-sided significance level = 2.5%
- Power = 80%
- Attrition = 30%

The sample size for this study was not determined by this endpoint.

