#### 11.1.4.3 Statistical Methods

The analysis for this endpoint will be performed once, either in conjunction with the interim analysis of Safety Endpoint 1, if the analysis of Safety Endpoint 1 is successful in rejecting the null hypothesis, or at the time of the final analysis of Safety Endpoint 1. The analysis for this endpoint will use the communication results taken at the 6 Month Visit and the communication success rate will be calculated using the data from all postures.

A repeated measure logistic regression will be fit with an indicator of communication success of each posture test as the response and subject as the repeated measure in an intercept only model to calculated the adjusted communication success rate and the 97.5% one-sided lower pointwise confidence limit. An unstructured correlation matrix will be used, unless a different structure is found to be more appropriate. The adjusted communication success rate and the 97.5% one-sided lower pointwise confidence limit by converting the intercept estimate and 97.5% one-sided upper pointwise confidence limit from the model previously described into an event rate and corresponding confidence limit. This adjusted 97.5% one-sided lower pointwise confidence limit of the communication success rate will compared to the performance goal of 88%. If the lower confidence limit exceeds 88%, the null hypothesis will be rejected. Please see the Statistical Analysis Plan (SAP) for more specifics. The unadjusted rate and 97.5% one-sided lower pointwise confidence limit and 97.5% one-sided using the one-sided Score methodology will also be presented as sensitivity analysis.

A subject-level evalution of the communication success rate across the four postures is being analyzed as an ancillary objective. See **Section 11.2**.

Missing posture testing data due to missed 6 Month Visits or a missing posture of the 4 tested will be considered missing data. To assess the potential impact missing data could have had on the analysis results, a tipping point analysis will be conducted. The tipping point analysis will assign each missing posture test as either a failure or success. All possible combinations of these posture tests' data will be evaluated along with the actual observed data to find the point, if any, at which the endpoint is failed.

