# 11.1.5.3 Statistical Methods

The analysis for this endpoint will be performed once, either in conjunction with the interim analysis of Safety Endpoint 1, if the analysis of Safety Endpoint 1 is successful in rejecting the null hypothesis, or at the time of the final analysis of Safety Endpoint 1. Two groups of subjects will be included in the endpoint evaluation: (1) PMA Sample cohort subjects with an EMPOWER PG PCT measurement taken at the 6 Month Visit (with a 0.4 ms pulse width), and (2) PMA Sample cohort subjects with a Major EMPOWER MPS System- and Procedure-related Complication between implant and 6 months due to an elevated threshold. The number of responders (PCT at 6 Month Visit  $\leq 2.0$  [contact] ms) divided by the total number of subjects included in the endpoint evaluation will be calculated. The one-sided 2.5% binomial exact lower confidence limit will be calculated and compared to the performance goal of 80%. If the lower confidence limit exceeds 80%, the null hypothesis will be rejected.

To assess the potential impact missing data could have had on the analysis results, a tipping point analysis will be conducted that will include subjects with the EMPOWER PG implanted. The tipping point analysis will assign each subject with missing data as

MODULAR ATP

Page 89 of 148

either being a PCT responder or a PCT non-responder. All possible combinations of these subjects' data will be evaluated along with the actual observed data to find the point, if any, at which the endpoint is failed.

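### The primary communication analysis has no rule for posture tests that are absent because a device was explanted for communication failure, so such failures can leave the success rate

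*Protocol*

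**What the plan says.** Protocol 11.1.4 sets the population: "The assessment will include subjects who are successfully implanted with both the EMPOWER PG and S-ICD". Section 11.1.4.3 calculates the rate from results taken at the 6 Month Visit and rejects the null if the adjusted 97.5% lower limit exceeds 88%. On absent tests it says "Missing posture testing data due to missed 6 Month Visits or a missing posture of the 4 tested will be considered missing data", and it adds a tipping point analysis that sets each absent test to failure or success. SAP 1.1 fits the model to subjects who are evaluable for the endpoint; the visible text does not define that term.

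Protocol 9.5 lists explant of the investigational devices as a reason for withdrawal and notes that "this provision includes explant of the EMPOWER PG in all subjects". Section 10.12 withdraws subjects whose Coordinated System is explanted, after at least 30 days. It keeps in follow-up subjects who still have the EMPOWER PG or an S-ICD with clinical firmware. Subjects who receive another device stay on their original schedule.

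Primary Effectiveness Endpoint 2 (11.1.5.3) is built differently. Beside subjects with a 6-month measurement, its evaluation includes "PMA Sample cohort subjects with a Major EMPOWER MPS System- and Procedure-related Complication between implant and 6 months due to an elevated threshold".

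**The concern.** Communication is the novel function of the system, and the study is single-arm against a fixed goal. Protocol 18.2 lists both communication failure and surgical revision or replacement of the system as risks, so the plan foresees removal of a system that does not communicate. If that happens before 6 months and no device is put back, no communicating pair is left to test. The subject then contributes no posture results and disappears from numerator and denominator. The loss is not random: it removes the worst outcomes on the very quantity being tested, and it can only push the rate up. Endpoint 2 shows that the plan recognises this problem for pacing threshold.

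**Working it through.** **1. Inputs.** Expected rate 95% and goal 88% (Synopsis table); one-sided 2.5%, power 80%, attrition 30% (11.1.4.2); four postures per subject (10.7.3.2); 134 and 223 subjects at the interim and final analyses of Safety Endpoint 1, when this endpoint is tested (11.1.1.2, 11.1.4.3).

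**2. The plan's own figure.** Section 11.1.4.2 requires "152 tests from a minimum of 38 subjects (220 tests including attrition" for attrition).

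- Normal approximation: n = [1.960·√(0.88·0.12) + 0.842·√(0.95·0.05)]² / 0.07² = 137.3.
- Continuity correction: (137.3/4)·[1 + √(1 + 2/(137.3·0.07))]² = 151.3, so 152 tests = 38 × 4.
- Attrition: 38/0.7 = 54.3, so 55 subjects and 220 tests.

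The stated figures reproduce.

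**3. Size of the bias.** Let p be the success rate among tested subjects and f the share whose tests are absent because of communication failure. Counting those as failures gives p(1 − f), so the reported rate is too high by p·f. With p = 95%:

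| f (assumed) | Rate with failures counted | Upward bias |
|---|---|---|
| 1% | 94.05% | 0.95 points |
| 2% | 93.10% | 1.90 points |
| 5% | 90.25% | 4.75 points |

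The rate falls to the goal at f = 1 − 0.88/0.95 = 7.4%.

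**4. False-pass rate.** Suppose the rate with such subjects counted as failures is exactly 88%. After dropping a share d, the rate among those left is 0.88/(1 − d): 88.89% for d = 1% and 89.80% for d = 2%. I simulated four correlated tests per subject (beta-binomial, intra-subject correlation 0.5 to 0.2; 40,000 runs per case) and compared the cluster-robust logit lower limit with 88%.

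| Share dropped (assumed) | 134 subjects | 223 subjects |
|---|---|---|
| 0% | about 2.5% | about 2.5% |
| 1% | about 5-7% | about 7-9% |
| 2% | about 12-16% | about 17-25% |

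The lower figure in each pair belongs to correlation 0.5. Repeat runs agree to about one point. The distortion grows with sample size because the bias is fixed while the limit tightens. For scale, 2% of 134 is 2.7 subjects.

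**5. How many added failures would overturn a pass.** Take about 95% observed success with isolated failures, and add subjects who fail all four postures. The limit is expit{logit(m) − 1.96·SE/[m(1 − m)]}, where SE = √Σ(yᵢ − 4m)²/(4N), yᵢ is subject i's number of successes, m the overall rate and N the number of subjects. The unadjusted score limit is in brackets.

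| Tested subjects | Limit with none added | Added subjects that bring it below 88% |
|---|---|---|
| 38 | 90.4% (90.0%) | 1 (1) |
| 134 | 93.0% (92.8%) | 5 (7) |
| 223 | 93.5% (93.3%) | 10 (13) |

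At 38, for example, 144/152 gives 90.4%; one added subject makes it 144/156, with a limit of 84.4% (87.0%).

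**The case against.** **The plan never says that explanted subjects are missing.** This stands as a point of wording. The quoted sentence speaks of missed visits and missed postures, and exclusion follows only when it is read with 9.5 and 10.12. The defect is an absent rule, not a stated wrong one.

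**Disabled communication or a replaced device might be thought to cause the same loss.** A reader might infer this, but the documents do not support it. With both devices in place the subject stays in follow-up (10.12), the four-posture test is still required (10.7.3.2), and its setup programs communication on (10.3.4.2). A subject with a replacement device follows the original schedule and is tested on the new device. How that result should count is a separate open question.

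**The tipping point analysis includes the case in which every absent test is a failure.** True, and it would expose the effect. But rejection under 11.1.4.3 depends only on the observed-data limit.

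**An explant already counts elsewhere.** System revision, including explant, is a major complication under Safety Endpoint 1 if adjudicated as related to the EMPOWER MPS or its procedure (11.1.1), and study success needs that endpoint too (11.5.1). This is a partial safeguard. It does not correct the communication rate.

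**The error rates in step 4 are conditional.** They use a stricter definition of success, a true rate exactly at the goal, and assumed shares and correlation. If the target is only the success of tests actually done at 6 months, the test keeps about 2.5%. At the expected 95%, step 5 shows that a pass at 134 or 223 subjects would survive several such failures.

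**The term evaluable may be defined in text not available here.** Section 11.3 and the SAP sample code are not visible. If a rule stands there, 11.1.4.3 should point to it.

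**Conclusion.** The concern holds for one defined group: subjects with a device explanted without replacement before 6 months because of communication failure, or permanently taken out of service so that it cannot be tested. Under the visible text they leave the primary analysis, and the bias is upward whenever such subjects exist. Endpoint 2 retains its analogous cases.

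The size is unknown, since the documents give no rate for such events. Under the assumptions of step 4, losing 1% to 2% of subjects turns a 2.5% error rate into roughly 5% to 25%, depending on sample size and correlation. Near the expected 95% the conclusion is robust at 134 or 223 subjects and fragile only near the 38-subject minimum. A reader might infer that the endpoint's type I error is already known to be inflated; the documents do not support that. They support an unspecified rule whose omission works in one direction and is cheap to close before analysis.

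**What to change.** In 11.1.4.3 and the SAP:

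1. State that posture tests absent because a device was explanted or permanently taken out of service for communication failure count as failures in the primary analysis. Identify the reason from the Device Tracking Form rationale or CEC adjudication. Say whether all four postures are scored as failed; since the test unit is the posture, this is a choice to be made in advance.
2. Define the evaluable subject to match.
3. State how a subject whose device was replaced for communication failure is scored.
4. Leave all other absent tests missing and subject to the tipping point analysis. Subjects with both devices in place and communication programmed off need no new rule, because 10.7.3.2 already requires their test.

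**Cost.** A few lines of text. Section 10.12 has the Device Tracking Form record explant, removal from service and permanent disabling, with rationale, so these cases should need no new data. It does not show that the form captures the separate mCRM communication setting, but the fix does not depend on that. The reported rate may be slightly less favourable.

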# 11.1.5.1 Hypotheses

H0: PCT Responders at 6-Month Visit is  $\leq 80\%$ 

HA: PCT Responders at 6-Month Visit is > 80%,

# 11.1.5.2 Sample Size

A total of 57 measurements (6-month [contact] ms) are required to sufficiently power the Primary Effectiveness Endpoint 2. The following assumptions were used to calculate the sample size:

- Performance goal = 80%
- One-sided significance level = 2.5%
- Power = 90%

The sample size for this study was not determined by this endpoint.

# 11.1.5.3 Statistical Methods

The analysis for this endpoint will be performed once, either in conjunction with the interim analysis of Safety Endpoint 1, if the analysis of Safety Endpoint 1 is successful in rejecting the null hypothesis, or at the time of the final analysis of Safety Endpoint 1. Two groups of subjects will be included in the endpoint evaluation: (1) PMA Sample cohort subjects with an EMPOWER PG PCT measurement taken at the 6 Month Visit (with a 0.4 ms pulse width), and (2) PMA Sample cohort subjects with a Major EMPOWER MPS System- and Procedure-related Complication between implant and 6 months due to an elevated threshold. The number of responders (PCT at 6 Month Visit  $\leq 2.0$  [contact] ms) divided by the total number of subjects included in the endpoint evaluation will be calculated. The one-sided 2.5% binomial exact lower confidence limit will be calculated and compared to the performance goal of 80%. If the lower confidence limit exceeds 80%, the null hypothesis will be rejected.

To assess the potential impact missing data could have had on the analysis results, a tipping point analysis will be conducted that will include subjects with the EMPOWER PG implanted. The tipping point analysis will assign each subject with missing data as

MODULAR ATP

Page 89 of 148

either being a PCT responder or a PCT non-responder. All possible combinations of these subjects' data will be evaluated along with the actual observed data to find the point, if any, at which the endpoint is failed.

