#### 6.6 Study Rationale

Patients may benefit from ventricular arrhythmia termination with ATP because it can avoid a shock that is often painful and consumes battery energy. The effectiveness of ATP therapy in terminating VT is well established and recognized by international guideline recommendations for ICD programming. Therefore, ATP therapy effectiveness is not the primary focus of the study. Instead, the MODULAR ATP Clinical Study will focus on the novel aspects of the mCRM Coordinated System for the delivery of ATP.

The MODULAR ATP Clinical Study evaluates the safety and effectiveness of the EMPOWER MPS and the unique aspect of the mCRM Coordinated System, which is the unidirectional transmission of conductive communication signals from the S-ICD System to the EMPOWER PG. The EMPOWER PG is designed to recognize communication signals sent from the S-ICD coil towards the S-ICD PG, creating a communicating vector. Because this communication can be affected by the orientation of the devices relative to each other, the primary effectiveness endpoint will demonstrate communication success in varied orientations by altering body postures of subjects. Communication is tested by commanding a communication signal from the S-ICD that results in EMPOWER pacing for 10 beats above the subject's intrinsic rate.

Additionally, communication success will be demonstrated during spontaneous ventricular tachyarrhythmia episodes.

The effectiveness of the EMPOWER PG will be assessed by measuring adequate Pacing Capture Threshold (PCT) during follow-up visits post-implant. PCT has been shown to be affected by multiple factors, including the method and stability of fixation. The EMPOWER PG is designed to deploy using 4 active-fixation nitinol talons, as compared to the conventional active-fixation screw or passive-fixation tine engagement used in a transvenous lead system. The MICRA leadless pacemaker uses a similar mechanism consisting of 4 active-fixation nitinol tines, but the NANOSTIM leadless pacemaker uses a different mechanism consisting of an active-fixation fixed screw. Results from other

<sup>15 Wathen M. Implantable cardioverter defibrillator shock reduction using new antitachycardia pacing therapies. *Am Heart J.* 2007 Apr;153(4 Suppl):44-52.

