<sup>16 Wilkoff BL, Fauchier L, Stiles MK, et al. 2015 HRS/EHRA/APHRS/SOLAECE expert consensus statement on optimal implantable cardioverter-defibrillator programming and testing. *Europace*. 2016 Feb;18(2):159-83.

<sup>17 [name], PhD, FHRS (Chair), [name], PhD, [name], FHRS, [name], FHRS, CCDS. 2019 HRS/EHRA/APHRS/LAHRS focused update to 2015 expert consensus statement on optimal implantable cardioverter-defibrillator programming and testing. *Heart Rhythm* 2019;17:220–228.

leadless pacemaker clinical trials showed that dislodgment was higher for the NANOSTIM leadless pacemaker as compared to the MICRA leadless pacemaker. In the LEADLESS trial studying the NANOSTIM leadless pacemaker, no device dislodgements were identified. However, there were six device dislodgements in the LEADLESS II trial. In comparison, there were no dislodgements in the MICRA IDE trial and only one occurred in the MICRA Post-Approval Study. The difference in dislodgement rate could be related to the difference in the fixation mechanism design between the two leadless devices. The fixation mechanism of the EMPOWER devices warrants evaluation in the pre-market clinical study.

The EMPOWER pacemaker uses a motion-based accelerometer to generate an electronic signal, which can be translated to a rate increase in proportion to the activity level of the patient. The rate response function will be evaluated during the trial due to the differences in the location of the accelerometer of an EMPOWER pacemaker, which resides inside of the heart chamber, compared to a transvenous pacemaker, which resides outside of the heart, usually in the infraclavicular or abdominal region.

Modern VVI(R) transvenous pacemakers are proven to be reliable in providing adequate pacing support. The reliability of the EMPOWER leadless pacemaker in providing appropriate pacing must be demonstrated before using it in pacemaker-dependent patients. Therefore, the MODULAR ATP Clinical Study protocol is designed to obtain data using Holter monitoring to support use of the EMPOWER PG in future pacemaker dependent patients.

Demonstration of the safety and effectiveness of the EMPOWER System in this study is required to obtain global market approval for commercial release. In addition, safety data collected may be used to support future post-market approval conditions mandated by global regulatory agencies.

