# 18.1 Risks Associated with the EMPOWER MPS

Potential adverse events and risks related to the EMPOWER MPS and the implantation of the EMPOWER PG may include, but are not limited to, the following:

- Aneurysm or pseudoaneurysm
- Allergic reaction
- Arterial injury
- Arteriovenous (AV) fistula
- Bleeding
- Bradycardia
- Breakage/ failure of instruments
- Cardiac arrest
- Cardiac injury, such as rupture, tear, or perforation, possibly resulting in pericardial effusion or cardiac tamponade
- Cerebrovascular accident
- Complications due to prolonged fluoroscopic radiation, such as skin burn
- Component failure

<sup>40 EMPOWER™ MODULAR PACING SYSTEM Leadless Cardiac Pacemaker with Delivery Catheter Physician's Technical Manual

MODULAR ATP

Page 102 of 148

- Damage to cardiac structures, such as tissue damage, valve damage, or coronary arterial constriction
- Death
- Device embolism
- Disabling device unintentionally
- Electrolyte imbalance/dehydration
- Elevated thresholds
- Embolism, such as pulmonary embolism
- Extracardiac (muscle/nerve) stimulation
- Fixation deformation and/ or breakage
- Fluid accumulation
- Foreign body reaction/ rejection phenomena
- Heart failure following chronic RV apical pacing
- Heart failure, worsening
- Hematoma or seroma
- Inability to communicate with device, including inability to reprogram
- Inappropriate or ineffective rate response
- Incision site complications, such as excessive fibrotic tissue growth
- Induction or acceleration of arrhythmia
- Infection, including endocarditis
- Local tissue reaction
- Loss of capture
- Nerve damage
- Oversensing/undersensing leading to loss of pacing or inappropriate pacing
- Pacemaker syndrome
- Pain
- Pericardial rub, effusion, or pericarditis
- Pulse generator dislodgment or migration
- Renal failure from contrast media
- Surgery for early replacement or implantation of a new device, such as due to premature battery depletion
- Syncope
- Thrombosis, such as deep vein thrombosis
- Tissue necrosis, such as myocardial infarction (MI)
- Toxicity
- Valve damage
- Vasovagal response
- Venous occlusion

- Venous trauma, such as perforation, dissection, or erosion
- Vessel spasm

Patients may develop psychological intolerance to a pulse generator and may experience the following:

- Dependency
- Depression
- Fear of premature battery depletion
- Fear of device malfunction

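### Primary Effectiveness Endpoint 2 omits subjects with no 6 Month PCT because the EMPOWER PG was lost to dislodgement, or to loss of capture not attributed to threshold, while counting the parallel elevated-threshold failures

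*Protocol*

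**What the plan says.** Protocol 11.1.5.3 forms the denominator from two groups in the PMA Sample cohort. Group 1 is subjects with a PCT measured at the 6 Month Visit at 0.4 ms. Group 2 is subjects with a Major EMPOWER MPS System- and "Procedure-related Complication between implant and 6 months due to an elevated threshold". The numerator is subjects whose 6 Month PCT meets the responder threshold, so a group 2 subject without that measurement counts as a failure. The one-sided exact lower limit is compared with 80%. A tipping-point analysis covers subjects with missing data, but the pass/fail rule does not refer to it.

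Section 6.6 explains why PCT was chosen: "PCT has been shown to be affected by multiple factors, including the method and stability of fixation". It adds: "The fixation mechanism of the EMPOWER devices warrants evaluation in the pre-market clinical study". Section 18.1 lists "Pulse generator dislodgment or migration" and loss of capture as potential events alongside elevated thresholds. Under 9.5 and 10.12, a subject whose system is explanted is followed for at least 30 days and withdrawn. A subject who receives another EMPOWER PG stays on the original visit schedule.

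The SAP text supplied adds nothing on this endpoint.

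**The concern.** Group 2 accepts that a device which fails before 6 months should count against the endpoint even though nothing can be measured at the visit. It does so for one cause only. A device that dislodges, is retrieved at month 2 and is not replaced also leaves nothing to measure, but the subject is left out of the calculation. PCT was chosen partly because it reflects fixation, and a dislodged device is the most direct fixation failure.

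This is not ordinary missing data, because the reason the value is missing is itself a failure of the device. Leaving these subjects out can only move the estimate upward. The endpoint is one of those that must pass for study success (11.5.1).

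**Working it through.** **The plan's own figure.** The synopsis row reads "PCT measurement. 95% 80% One-Sided Lower Confidence Limit 2.5% 90% 57 30% 82", and 11.1.5.2 says that 57 measurements "are required to sufficiently power the Primary Effectiveness Endpoint 2". Inputs: goal p0 = 0.80, expected p1 = 0.95, one-sided alpha 0.025, power 0.90.

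- Normal approximation: n0 = [(1.96·√(0.80·0.20) + 1.2816·√(0.95·0.05)) / 0.15]² = 50.2.
- With continuity correction: n = (n0/4)·[1 + √(1 + 2/(n0·0.15))]² = 56.7, rounded up to 57.
- Exact rule at n = 57: pass with at least 52 responders; alpha 0.0186, power 0.935.
- Attrition: 57/0.70 = 81.4, rounded up to 82.

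The stated sample size reproduces and is not in dispute.

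**Who is left out.**

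| Situation before the 6 Month Visit | 6 Month PCT? | Where counted |
|---|---|---|
| Lost, elevated threshold (Major complication) | No | Group 2, non-responder |
| Lost, dislodgement or migration, not replaced | No | Neither group |
| Lost, loss of capture not attributed to threshold, not replaced | No | Neither group |
| Repositioned or replaced, measured at visit | Yes | Group 1 |
| Still implanted and testable, poor capture | Yes | Group 1, likely non-responder |

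Only the second and third rows are at issue.

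**Effect on the limit.** The exact lower limit for x responders of n is the 0.025 quantile of Beta(x, n − x + 1). I use n = 134 and 223, the Safety Endpoint 1 interim and final counts, because this endpoint is tested at one of those analyses. I assume no other missing data.

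| Lost devices | Excluded (as written) | Counted as non-responders |
|---|---|---|
| 1 of 134 | 116/133: 80.3%, pass | 116/134: 79.6%, fail |
| 4 of 134 | 114/130: 80.8%, pass | 114/134: 77.9%, fail |
| 6 of 134 | 112/128: 80.5%, pass | 112/134: 76.2%, fail |
| 1 of 223 | 190/222: 80.3%, pass | 190/223: 79.9%, fail |
| 6 of 134, near the planned rate | 122/128: 90.1%, pass | 122/134: 84.9%, pass |

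The first four rows were placed at or close to the pass boundary. The last is close to what the plan expects. With a true 95% rate among measured subjects, the two rules give different decisions in about 0.5% of trials with 4 losses and 2.7% with 6.

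**Error rate if losses are failures.** Suppose the success rate with losses counted as failures is exactly 80%. With a loss share L, the rate among measured subjects is 0.80/(1 − L); for L = 5% this is 0.80/0.95 = 84.2%. The chance of passing under the written rule, with the denominator rounded to n(1 − L), is:

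| L | n = 134 | n = 223 |
|---|---|---|
| 1% | 3.4% | 4.2% |
| 3% | 6.9% | 12.6% |
| 5% | 19.6% | 29.3% |
| 7% | 41% | 55% |

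The nominal level is 2.5%. The loss shares are assumptions. Section 6.6 reports dislodgement counts in other devices' trials without denominators, so it gives no rate. The value 7% is the complement of the planned 93% complication-free rate for all major complications, so it is a ceiling under the plan's own expectation.

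**The case against.** The strongest reply is that the gap is narrow and its consequences largely covered elsewhere. Several parts of this stand.

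- A reader might infer that every device lost to dislodgement or loss of capture leaves the denominator. The documents do not support that. Replaced, repositioned or still-testable devices remain on schedule and are measured (10.7.1, 10.12).
- Some loss of capture is itself an elevated threshold. Section 10.3.1.7 defines the threshold from the level at which capture is lost, and the group 2 wording is a test of cause. Dislodgement is the clearer case.
- A reader might infer that inclusion depends on which event term a site picks. Section 18.1 is a list of potential risks, not a coding dictionary, and the events committee adjudicates under a charter not supplied here. Section 11.3, which may define the PMA Sample cohort, is also not in the supplied text. Neither absence is counted as a defect.
- A device- or procedure-related loss that leads to revision, hospitalization or permanent loss of function counts against Safety Endpoint 1, which must also pass. With a log-log limit at the interim alpha of 1.2% and no censoring, that endpoint passes at 134 subjects with at most 9 major complications of all kinds. The larger loss shares above would therefore tend to fail the study anyway.
- The tipping-point combinations include the case where every lost device is a non-responder.

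Two parts do not answer the point. Safety Endpoint 1 has a different goal and mixes all major complications, so it does not correct the effectiveness estimate. The tipping-point analysis has no stated bearing on the decision and treats a known failure as a value that might equally have been a success.

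**Conclusion.** The gap is real and limited. Subjects without a 6 Month PCT because the device was removed, abandoned or permanently disabled for dislodgement or migration, or for loss of capture not attributed to threshold, drop out of the primary analysis. The responder rate and its lower limit are then biased upward.

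Near the 80% goal a single such subject can reverse the decision. At the planned 95% rate with 134 or more subjects the decision is unlikely to change, although the reported rate would still be somewhat too high. A reader might infer from the boundary examples that the endpoint is likely to pass wrongly; the plan's own expected rate does not support that. The size rests on an assumed number of losses, for which the documents give no figure.

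**What to change.** In 11.1.5.3, widen group 2 to subjects without a 6 Month PCT whose EMPOWER PG was removed, abandoned or permanently disabled before the 6 Month Visit because of elevated threshold, loss of capture, or dislodgement/migration, using the cause adjudicated by the Clinical Events Committee. State that they are non-responders in the primary analysis.

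Leave subjects with a measured 6 Month PCT in group 1, including those repositioned or replaced. Scoring them as non-responders despite an adequate measurement would turn the endpoint into a composite, which the responder definition does not support. Keep losses for unrelated reasons as missing in the tipping-point analysis.

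The change is one of wording. It should need no new visits, since device-related events already go to the committee. The cost is a slightly lower reported rate and some power. With 95% responders among measured subjects and assumed losses of 1, 3, 5 and 7%, power is 99.9, 98, 90 and 70% at n = 134, and 100, 100, 99 and 91% at n = 223. At the minimum of 57 it would be 88, 71, 51 and 33%, so the minimum should be rechecked if it is to stand alone.
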